### **6.2.2 24-Hour Post-Feeding Visit (Day 1 +1 day)**

All Cohort A participants will return for a 24-hour post-feeding visit. At this visit, the following procedures will be performed.

- Vital Signs.
- Clinician assessment of bites and biopsy sites.
- Blood draw for research labs (section 7.2, Appendix A).

### **6.2.3 Final study contact (Day 7 ±3 days)**

All participants will be contacted by telephone about 1 week after Day 0 to ensure there are no issues after the feedings or biopsies or adverse events. Any participant who experiences complications due to feeding or biopsies will be examined in the clinic and followed until complications have resolved and/or referral to the necessary medical care has been made. After this phone call, Cohort A participation will be complete.

## **6.3 Cohort B**

Cohort B participants will undergo 4 vector feedings over about 8 weeks and 3 biopsy procedures after the fourth and final feeding.

### **6.3.1 Vector feeding and biopsy (Days 0, 14, 28, and 42, ±7 days)**

All Cohort B participants will undergo feeding procedures on Days 0, 14 (±7 days), 28 (±7 days), and 42 (±7 days) for a total of 4 feedings. Feedings will be approximately 2 weeks apart with a minimum of 7 days in between feedings. These visits will occur in the SCSU, or other appropriate unit, and the following procedures will be performed:

- Review of medical/medication history.
- Review of inclusion/exclusion criteria.
- Documentation of usual responses to mosquito bites as none (0), mild (1), moderate (2), or severe (3). (only performed on Day 0).
- Clinician exam/assessment.
- Vital signs.
- Urine pregnancy test (for women of childbearing potential; confirmed negative before feeding).
- Blood draw for research labs (section 7.2, Appendix A).

After these procedures, participants will undergo feeding with the assigned vector. Feeding and monitoring will be conducted as described in section 5.1.

After each feeding on Day 0, 14, and 28, participants will be monitored for a minimum of 1 hour post feeding and the following procedures will be performed:

- Any clinical tests that are medically indicated or appropriate to ensure the safety of the individual participant as deemed by the PI.
- Participants will be asked to not apply any topical steroid treatments. Other topical treatments, such as antihistamines, may be applied as needed.

After the final feeding on Day 42, the following procedures will be performed:

- 2 skin punch biopsy collections as follows:
  - 1 biopsy from bitten skin collected no earlier than 3.5 hours and no later than 4.5 hours after the vector feeding is completed.
  - 1 biopsy from unbitten skin on the opposite arm collected no earlier than 30 minutes and no later than 6 hours after the vector feeding is completed.
- Any other clinical tests that are medically indicated or appropriate to ensure the safety of the individual participant as deemed by the PI.
- Participants will be asked to not apply any topical treatments after the fourth and final feeding. Other topical treatments may be applied after the Day 44 biopsy is completed.

Following these study procedures, participants will be allowed to leave as long as there are no safety concerns. They will be provided with medications if needed before they leave, and they will be asked to notify the study team if they have any reactions or side effects.

### **6.3.2 Follow-up and biopsy (Day 44 +3 days)**

About 2 days after the final feeding procedure, all participants in Cohort B will return to the NIH CC for a follow-up visit. The following procedures will be performed:

- Vital signs.
- Review of medical/medication history.
- Clinician assessment of bite and biopsy sites.
- 1 skin punch biopsy from bitten skin at a minimum 40 hours after vector feeding is completed.
- Blood draw for research labs (section 7.2, Appendix A).

Following these study procedures, participants will be allowed to leave as long as there are no safety concerns. They will be provided with medications if needed before they leave, and they will be asked to notify the study team if they have any reactions or side effects.

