#### 3.2 Study Endpoints

##### 3.2.1 Primary endpoints

- Measurement of changes in the early innate immune response and cellular recruitment in the skin of bitten versus unbitten skin in each vector group in Cohort A by:

- a. immunohistochemistry of target proteins in vector-naïve participants for each of the three vector groups at 30 minutes and 4 hours after 1 feeding/exposure. Biopsies from eight participants within a group will be assigned for immunohistochemical analysis.
  - b. Transcriptomics via deep sequencing and/or gene expression array of cDNA libraries made from skin RNA of vector-naïve participants for each of the three vector groups at 30 minutes and 4 hours after 1 feeding/exposure. Biopsies from seven participants within a group will be assigned for transcriptomic analysis.
2. Measurement of changes in the adaptive immune response and cellular recruitment in the skin of bitten versus unbitten skin after fourth and final feeding in each vector group in Cohort B by:
    - a. immunohistochemistry of target proteins in vector-experienced participants for each of the three vector groups at 4 hours and 48 hours after 4 feedings/exposures. Biopsies from eight participants within a group will be assigned for immunohistochemical analysis.
    - b. Transcriptomics via deep sequencing and/or gene expression array of cDNA libraries made from skin RNA of vector-experienced participants for each of the three vector groups at 4 hours and 48 hours after 4 feedings/exposures. Biopsies from seven participants within a group will be assigned for transcriptomic analysis.

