### **3.2.2 Secondary endpoints**

1. Flow cytometry analysis of PBMCs and cytokine analysis of plasma collected 24 hours after the one feeding in each vector group of vector-naïve participants in Cohort A.
2. Flow cytometry analysis of PBMCs and cytokine analysis of plasma collected 48 hours after the fourth and final feeding in each vector group of vector-experienced participants in Cohort B.

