  - a. 5-10 female insects will be aspirated or placed into a secured feeding device prior to feeding and brought to the CC from the LMVR Insectary.
- iii. The feeding site will be wiped clean with mild unscented soap and water and the device will be placed on the participant's arm for up to 20 minutes. The insects will feed through a disposable mesh on the bottom of the feeding device. This device permits the evaluation of feeding on

the human participant at the end of exposure, where the abdomen of blood fed mosquitoes or sand flies will be distended and bright red, and clearly visible through the mesh.

- a. In the unlikely event of no feeding or poor feeding (only 0-2 insects fed or probed as noted by trained staff), the participant may undergo a repeat feed with 5-10 fresh insects once.
  - b. If a repeat feed is required, the post-feeding biopsies and blood draws will be done based on the timing of the repeat feed.
  - c. Post-feeding times will be calculated from the time the feeding device is removed.
- iv. Post-feeding, redness, swelling and number of visible bites will be assessed and documented immediately (+15 minutes) and 30 minutes (+15 minutes) after the feeding device is removed. This may also include taking photographs of the bites.
  - v. Once the mosquitoes or sand flies have fed, they will be brought back to the lab for evaluation and then disposal.

After each feeding, participants may be offered standard treatment as needed to control reactions to vector bites. These treatments may include cold compresses, topical or oral antihistamines, or topical steroids. On days when biopsies will be performed, necessary treatment to control the reaction to the vector bite will be offered after the biopsy is completed. Any necessary treatment to control bleeding, discomfort, or reduce scarring from the biopsy will also be offered.

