### **11 Remuneration Plan**

Participants will be compensated according to Table 2 below. Study visits will be compensated according to the number of visits the participant completes. Participants will only be compensated for the protocol visits and interim visits requested by the investigators if the visits are medically necessary. Remuneration will be provided to the participants in Cohort A after the completion of the day 7 phone call. Remuneration will be provided to participants in Cohort B two times: after the completion of Day 28 and the remainder of the compensation will be provided after the day 51 phone call.

If a subject participates in Cohort A and Cohort B of the same vector, he/she will undergo Day 0 Feeding only once as part of Cohort A (which will also count for Day 0 Feeding for Cohort B). Therefore, these participants will not be compensated for Day 0 of Cohort B. They will receive compensation for the other protocol visits as described above and outlined below.

**Table 2.** Estimated participant remuneration.

Cohort A	Compensation
Day 0: Vector feeding and biopsy	\$825
Day 1: 24-hour post-feeding blood draw	\$100
Expected total for completion of Cohort A study visit	\$925
Cohort B	
Day 0: Vector Feeding 1	\$325
Day 14: Vector Feeding 2	\$425
Day 28: Vector Feeding 3	\$425
Day 42: Vector Feeding 4 and biopsy	\$725
Day 44: 48-hour post-feeding biopsy and blood draw	\$200
Expected total for completion of ALL Cohort B study visits	\$2100
Investigator-requested interim visits:	\$75

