 One biopsy from bitten skin will be collected no earlier than 3.5 hours and no later than 4.5 hours after the vector feeding is completed. One biopsy from unbitten skin on the opposite arm will be collected no earlier than 30 minutes and no later than 6 hours after the vector feeding is completed.

One biopsy will be collected from bitten skin at a minimum 40 hours after vector feeding is completed.

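### The Cohort B 48-hour primary biopsy has a 40-hour minimum but no maximum in hours, and its visit window lets it run to about 120 hours after the fourth feeding

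*Combined protocol and SAP*

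**What the plan says.** Section 3.2.1 sets the Cohort B primary endpoints, by immunohistochemistry and by transcriptomics, "at 4 hours and 48 hours after 4 feedings/exposures". It assigns biopsies from eight participants per vector group to the first assay and from seven to the second.

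Section 6.3.2 governs the later of the two bitten-skin biopsies. Its heading gives the visit as Day 44 +3 days, and the text places it "About 2 days after the final feeding procedure". The timing rule for the biopsy is "1 skin punch biopsy from bitten skin at a minimum 40 hours after vector feeding is completed". Appendix A has the same +3-day window in the column heading, and its footnote 6 reads "One biopsy will be collected from bitten skin at a minimum 40 hours after vector feeding is completed".

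Three other places bear on where the clock starts. Section 5.1 says "Post-feeding times will be calculated from the time the feeding device is removed". After a repeat feed, "the post-feeding biopsies and blood draws will be done based on the timing of the repeat feed". Table 2 in section 11 lists the visit as "Day 44: 48-hour post-feeding biopsy and blood draw".

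The secondary endpoint in section 3.2.2 uses "plasma collected 48 hours after the fourth and final feeding". That blood is drawn at the same visit, and section 6.3.2 gives the draw no limit in hours at all.

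On analysis, section 14.1 identifies the late Cohort B biopsies by nominal day (Day 44). Section 14.2 compares bitten skin at a given timepoint with unbitten skin from the same person.

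**The concern.** The endpoint names a time in hours, but the procedure that delivers it fixes only the early side in hours. The late side is left to a visit window stated in days. A sample taken four or five days after the fourth feeding would meet the written rule and still belong to the primary 48-hour contrast.

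The design itself treats time since the bite as informative, since 4 hours and 48 hours are separate primary timepoints in this cohort. If samples taken at two days and at five days are pooled under one label, the estimate describes neither time. The spread due to timing is then mixed with the differences between people that section 14.2 says are unknown and that the study hopes to describe. With 7 or 8 participants per contrast, very few late samples are needed for this to matter.

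**Working it through.** **Inputs**

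| Item | Value | Source |
|---|---|---|
| Nominal time of late biopsy | 48 h | 3.2.1 |
| Earliest time | 40 h | 6.3.2; Appendix A footnote 6 |
| Latest time in hours | none stated | 6.3.2; Appendix A footnote 6 |
| Visit window | Day 44 +3 days | 6.3.2; Appendix A |
| Fourth feeding | Day 42 ±7 days | 6.3.1; Appendix A |
| Time zero | removal of the feeding device | 5.1 |
| Participants per vector | 8 (immunohistochemistry), 7 (transcriptomics) | 3.2.1 |

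**1. Reproduce the plan's figure.** (44 - 42) x 24 = 48 h. This matches the stated endpoint time.

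**2. Decide where the window starts.** Two readings are possible.

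- From the actual fourth feeding: the window opens at 48 h nominal (the floor is 40 h) and closes at (44 + 3 - 42) x 24 = 120 h.
- From Day 0: a fourth feeding on Day 35 would put the visit at (44 - 35) x 24 = 216 h to (47 - 35) x 24 = 288 h. A fourth feeding on Day 49 would put it at (44 - 49) x 24 = -120 h to (47 - 49) x 24 = -48 h, that is, before the feeding.

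The Day 0 reading is unworkable. The Day 49 case alone shows this, so the result does not depend on feedings being allowed early. The fourth-feeding reading also agrees with the wording of sections 5.1, 6.3.2 and 11, and is used below.

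**3. Allowed deviation from 48 h.**

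- Early: 48 - 40 = 8 h.
- Late: 120 - 48 = 72 h.
- Ratio at the late end: 120 / 48 = 2.5.

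The 120 h is a day count at the same clock time. If clock times on the two days differ by up to 8 h (an assumption), it becomes 112 to 128 h.

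**4. Compare with the other biopsies** (6.2.1, 6.3.1, Appendix A footnotes 4 and 5).

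| Biopsy | Written limits | Latest minus nominal | Latest / nominal |
|---|---|---|---|
| Cohort A, 30 minutes | 30 to 90 min | 60 min | 3 |
| Both cohorts, 4 hours | 3.5 to 4.5 h | 0.5 h | 1.125 |
| Unbitten control | 0.5 to 6 h | no nominal time | not applicable |
| Cohort B, 48 hours | 40 h minimum only | about 72 h, by visit window | about 2.5 |

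**5. Weight of one sample.** With equal weighting, 1/7 = 14.3% and 1/8 = 12.5% of a contrast.

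**6. Illustration.** Assume k biopsies are taken at 120 h and all others at exactly 48 h. The mean sampling time is [(n - k) x 48 + k x 120] / n.

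| n | k = 1 | k = 2 |
|---|---|---|
| 7 | (288 + 120) / 7 = 58.3 h | (240 + 240) / 7 = 68.6 h |
| 8 | (336 + 120) / 8 = 57.0 h | (288 + 240) / 8 = 66.0 h |

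**7. Does the analysis plan deal with it?** Section 7.1.3 has the time and date of each biopsy time-out recorded, so actual hours can be recovered. Section 14 does not mention actual hours, a time covariate or a rule for late samples. The only labels it offers for this biopsy are the nominal day and the timepoint.

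**The case against.** The strongest reply has four parts.

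First, there is an upper bound, and 120 hours is its extreme. The text aims for about two days, Table 2 calls the biopsy a 48-hour one, and most visits may fall close to that. This is fair as a statement of intent, but an approximate phrase sets no maximum, and the section heading still admits a visit three days after Day 44.

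Second, the biopsies with limits in hours are taken on the feeding day, while the participant is on site. The late one needs a return visit, where a window in days is natural. Cohort A's 24-hour blood draw is handled the same way: Day 1 +1 day allows up to 2 x 24 = 48 h, twice nominal. This explains how the gap may have arisen. It does not close it, and the Cohort A draw has a similar weakness. It is also true that the 30-minute biopsy is looser in ratio (3 against 2.5), but it can be only one hour late and its limit is written down.

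Third, silence in section 14 is not a statement that actual times will be ignored. That stands: the analyst could use the recorded times. The plan does not commit to it, however, and gives a late sample no other timepoint to belong to.

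Fourth, no harm is shown. The study is described as highly exploratory, the sampling-time figures rest on an assumed number of late biopsies, mean sampling time is not an endpoint, and in a negative binomial model a pair's influence need not be 1/n. All of this is correct. It limits the weight of the point and rules out any statement about bias or power, but it does not remove the mismatch between the endpoint and the window.

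**Conclusion.** The concern holds. The primary endpoint is stated at 48 hours, while the written rules allow sampling from 40 to about 120 hours after the fourth feeding. The upper figure rests on counting the visit window from the actual fourth feeding, the only reading that works across the feeding window. The point concerns what the plan permits, not when biopsies were in fact taken. The number of late samples is unknown. The documents give no time course for this response in human skin, so neither the direction nor the size of any bias can be derived. The change should be made because the label of a primary contrast is at stake, the groups are small and the correction is inexpensive. The exploratory aim of the study keeps the point from ranking higher.

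**What to change.** In section 6.3.2 and in Appendix A (Day 44 column and footnote 6), state that the window runs from removal of the feeding device at the actual fourth feeding, including a repeat feed. Add an upper limit in hours around 48, chosen by the sponsor, for the biopsy and for the blood drawn at the same visit.

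In section 14.2, derive actual hours since feeding from the recorded time-out times and the time of device removal. Keep late biopsies in the data, show the actual hours, and report the 48-hour contrast with and without samples beyond the limit.

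The cost is wording in three places and a small sensitivity analysis. Biopsy times are already documented, so little or no new data collection is needed. The drawback is less freedom in scheduling the fourth feeding and the return visit. With 7 or 8 participants the with-and-without comparison can only be descriptive.

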### **6.3.3 Final study contact (Day 51 ±3 days)**

All Cohort B participants will be contacted by telephone about 1 week after Day 44 to ensure there are no issues after the feedings or biopsies or adverse events. Any participant who experiences complications due to feeding or biopsies will be examined in the clinic and followed until complications have resolved and/or referral to the necessary medical care has been made. After this phone call, Cohort B participation will be complete.

#### **6.3.4 Early termination visit**

- Discussion to review reason for termination.
- Review of medical/medication history.
- Review of inclusion/exclusion criteria.
- Clinician exam/assessment.
- Vital signs.
- Blood draw for research labs (section 7.2, Appendix A) if participant is willing.

#### **6.4. Unexpected or incidental medical conditions of the participant**

If unexpected or incidental medical conditions are diagnosed during the medical evaluation in this protocol, the participant will be referred to an appropriate physician and/or hospital and encouraged to follow up for treatment of their condition. Standard of care treatment may be offered by the study team if necessary while the participant is being referred to appropriate outside medical care.

### **7 Study Procedures/Evaluations**

See Appendix A for schedule of clinical and study procedures and laboratory evaluations. Blood volumes are provided in a tabular form in Appendix B: Blood Volumes for Specimen Collection.

#### **7.1 Study Procedures**

##### **7.1.1 Vital signs**

Participants must be sitting for a minimum of 5 minutes prior to these procedures being performed. Vital signs include blood pressure, mean arterial pressure, heart rate, respiratory rate, temperature, weight, and pulse oximetry. Height will be taken at the Day 0 visit only. On feeding days, vital signs will be performed pre-feeding.

##### **7.1.2 Arthropod Feeding**

Please see Section 5.1 (Arthropod Feeding)

##### **7.1.3 Skin biopsies**

From each participant, three 3-mm skin biopsies will be taken, two at the bite sites and one at an unbiten site on the opposite arm (control), using the following procedure:

1. Participant will be placed in a relaxed position with their arm out to expose the insect bites or control site on the ventral side of the appropriate forearm.
2. A time-out will take place where the participant's name and medical record number and the site of the biopsy will be confirmed. The time and date of the time-out will be documented.

3. Non-sterile gloves will be worn and pads will be laid out to protect clothing as needed.
4. Biopsy location will be marked with small circle.
5. 2% lidocaine with or without epinephrine will be drawn up in a 3-mL syringe.
6. A 30-gauge needle will be used to inject lidocaine: It will be inserted into the skin just outside the circle drawn around the biopsy site; 1-1.5 cc of lidocaine will be injected slowly.
7. Anesthesia will be tested using sharp forceps. More lidocaine will be injected as needed to achieve proper local anesthesia.
8. Chlorhexidine swabs will be used to disinfect the biopsy site by wiping concentrically from the center of the site to the outside of biopsy site.
9. A steri-drape may be applied around the biopsy site.
10. The biopsy will be performed by pulling skin taut with thumb and forefinger above and below the marked area. A punch biopsy tool will be used to apply pressure and turned back and forth 360 degrees. Forceps will be used to pull out the biopsy. Scissors may also be used if necessary to cut the specimen from the subcutaneous tissue.
11. Pressure will be held at the site using gauze, and then the site will be cleaned and dressed appropriately.
12. Sutures may be placed if deemed necessary by the clinical team. If sutures are placed, the participant will return to clinic approximately 10 days later for suture removal.

## **7.2 Laboratory Evaluations**

### **7.2.1 Safety laboratory evaluations**

For women of childbearing potential, a urine pregnancy test will be performed before each vector feeding procedure.

### **7.2.2 Laboratory testing of samples for study endpoints**

#### **Primary Endpoints:**

- Immunohistochemistry of target proteins in vector-naïve participant skin biopsy samples for each of the three vector groups at 30 minutes and 4 hours after the one feeding.
- Transcriptomics via deep sequencing and/or gene expression array of cDNA libraries made from skin RNA of vector-naïve participants for each of the three vector groups at 30 minutes and 4 hours after the one feeding.

- Immunohistochemistry of target proteins in vector-experienced participant skin biopsy samples for each of the three vector groups at 4 hours and 48 hours after the fourth and final feeding.
- Transcriptomics via deep sequencing and/or gene expression array of cDNA libraries made from skin RNA of vector-experienced participants for each of the three vector groups at 4 hours and 48 hours after the fourth and final feeding.

**Secondary Endpoints:**

- Flow cytometry analysis of PBMCs and cytokine analysis of plasma collected 24 hours after the one feeding of in each vector group of vector-naïve participants.
- Flow cytometry analysis of PBMCs and cytokine analysis of plasma collected 48 hours after the fourth and final feeding in each vector group of vector-experienced participants.

